8.8 Coronavirus Disease 2019 (COVID-19) Risk/Benefit Assessment

This study is to be conducted in healthy adult participants who are deemed not to be at higher risk of COVID-19 as per the latest version of the National Health Service (NHS) Guidance (<https://www.nhs.uk/conditions/coronavirus-covid-19/people-at-higher-risk/whos-at-higher-risk-from-coronavirus/>).

The safety of the participant is the primary concern; this study is to be conducted at Simbec-Orion Clinical Pharmacology Unit which is a Phase I accredited unit with extensive experience in conducting Phase I trials of similar design. Simbec-Orion prioritise the health and wellbeing of their clinical trial participants and, as such, have implemented a number of COVID-19 policies and risk mitigating actions. Prior to attendance at site, participants will be contacted to ensure they are not displaying any COVID-19 symptoms; Site COVID-19 policies will be explained to them at this time. Where appropriate perspex screens are in place and appropriate social distancing is enforced, when this is not possible, appropriate personal protective equipment (PPE) will be worn.

Simbec-Orion Clinical Pharmacology unit is a dedicated trial facility and, as such, staffing levels will not be affected by the potential burden presented by COVID-19 to other medical facilities. All employees present at the clinical site are aware of the COVID-19 specific working requirements and will work to the relevant 'Working Safely' Policy.

Medicines and Healthcare products Regulatory Agency (MHRA) Phase I Accreditation requirement No. 3 details the requirement for an agreement with a local hospital for supporting emergencies arising from the clinical trials performed by Simbec-Orion, this agreement is in place with Cwm Taf Morgannwg University Health Board and Prince Charles Hospital (PCH) for this purpose. Cwm Taf Morgannwg University Health Board and PCH have confirmed capacity to support any acute serious AEs (SAEs) during the COVID-19 pandemic (details contained within the latest version of the Simbec-Orion Clinical General Risk Assessment).

AX-158 did not suppress acute immune responses in pre-clinical murine models involving either the immune-dominant vaccinia peptide B8R or haptenated antigens. However, the effect of AX-158 on human immune surveillance, including the response to vaccination, is unknown. All participants will remain in-house for the duration of the study under the medical supervision of the PI throughout.

In addition, the sponsor has conducted a risk assessment in consideration of the ongoing COVID-19 vaccine deployment programme including assessment of the potential risks associated with concomitant vaccination whilst participating in this trial.

The sponsor has determined that the outcome of the risk assessment undertaken in conjunction with the study team is as follows. Knowledge on the Investigational Medicinal Product (IMP) is currently insufficient to assess the potential impact of IMP on the efficacy of COVID-19 vaccination or to assess the impact of COVID vaccination on IMP safety. If given concomitantly, it could possibly be difficult to discriminate if the AEs observed during the study are due to the IMP or due to COVID-19 vaccine. In addition, the study participants are young healthy volunteers, by definition without any co-morbidity, and are in consequence in a category of subjects without any immediate risk of developing a severe form of COVID-19, and not considered the top priority for the UK vaccine campaign.

Therefore, participants will be required to be fully vaccinated according to current Welsh / UK government guidelines prior to admission into the study. Participants are not permitted to have their COVID-19 vaccine injections (boosters) whilst in the study (from 28 days prior to dosing to completion of final post-study follow up procedures). Participants will be informed that if they are invited to receive a COVID-19 vaccination during the study and wish to receive the vaccine that they will be withdrawn from participation in the study. The investigator will check that any participants who may have a pre-booked appointment for a COVID-19 vaccination, are not in breach of this requirement.

Both the Study and Site Risk Assessments will be continually monitored and updated throughout the trial, and it is currently deemed acceptable to conduct the trial without it impacting or being impacted by the COVID-19 pandemic.

9 STUDY OBJECTIVES

9.1 Primary Study Objective

- To assess the safety and tolerability of single and multiple ascending doses of AX-158 when administered to healthy participants (Part A and Part C).

9.2 Secondary Study Objective

- To investigate the PK of single and multiple doses of AX-158 in healthy participants (Part A and Part C).
- To investigate any food effect on the PK of AX-158 following oral administration of a single dose to healthy participants (Part B).

10 INVESTIGATIONAL PLAN

10.1 Overall Study Design and Plan

This is a phase I, randomised, double-blind, placebo-controlled study to investigate the safety, tolerability, and PK of AX-158 in healthy male participants following single (Part A) and multiple (Part C) ascending doses including food effect (Part B).

The study will be conducted in three parts (Part A, Part B and Part C).

Part A (SAD) will enrol 8 participants per cohort randomised (3:1) to receive AX-158 (6 participants) or placebo (2 participants). Part A will follow a single ascending dose (SAD) design with all participants receiving one dose of AX-158 (or placebo) in the fasted state. Part B (Food Effect) will be conducted in 8 participants in a cross-over manner; each participant will receive AX-158 in the fed and fasted state. Part C (MAD) will enrol 8 participants per cohort randomised to (3:1) to receive AX-158 (6 participants) or placebo (2 participants).

Part C will follow a MAD design with participants receiving AX-158 (or placebo) once daily for 10 consecutive days, in a fed or fasted state (depending on the outcome of the Part B Food Effect). Doses, dosing duration and dose regimen (i.e., q.i.d., b.i.d., t.i.d.) of AX-158 and matching placebo for Part C may be modified based on all available safety, tolerability, and PK data and applied to additional MAD cohorts.

Up to one hundred and four (104) healthy participants are planned to be enrolled in this 3-part, multi cohort study. Part A (SAD) will be conducted in up to forty (40) participants (5 cohorts of 8 participants). Part B (Food Effect) will be conducted in 8 participants in a cross-over manner. Part C (MAD) will be conducted in up to twenty-four (24) participants (3 cohorts of 8 participants). Each participant will be assigned to only one study part and within each part, assigned to only one cohort.

Participants in Part A (SAD) will undergo a screening period (Day -28 to Day -2), an in-house treatment period comprising 4 overnight stays (from Day -1 to Day 4) and a follow up visit 5-7 days following administration of AX-158 or placebo.

Participants in Part B (Food Effect) will undergo a screening period (Day -28 to Day -2), two in-house treatment periods comprising of 4 overnight stays (from Day -1 to Day 4) separated by a minimum of 7 days between doses and a follow up visit 5-7 days following the final administration of AX-158.

Participants in Part C (MAD) will undergo a screening period (Day -28 to Day -2), an in-house treatment period comprising 13 overnight stays (from Day -1 to Day 13) and a follow up visit 5-7 days following the final administration of AX-158 or placebo.

For Part A (SAD) and Part C (MAD), a dose leader design will be implemented with 2 participants being dosed on the first dosing day of each cohort. Of these 2, 1 will be on active drug and 1 on placebo. The remainder of the cohort will be dosed at least 24 h later pending an acceptable safety profile in the dose-leader group and will contain at least 1 additional placebo participant. This design allows maintenance of the “blind” while also staggering ongoing exposure within the MAD phase.

In both Part A (SAD) and Part C (MAD), sequential cohorts will be exposed to increasing doses of AX-158. Prior to dose escalation between cohorts, safety and PK data from the previous

cohort will be reviewed by the DERC to determine whether it is appropriate to proceed to the next cohort/dose level.

The maximum dose level administered will not exceed a level anticipated to result in plasma exposures greater than those seen at the NOAEL, without prior approval by the REC and MHRA, as per Section 6.4.4 of the ICH E6 (R2) guidelines^[2].

The clinical phase is anticipated to take place between September 2021 and May 2022. The conclusion of the study is defined as last participant last visit.

The study will take place in the Clinical Unit of Simbec-Orion Clinical Pharmacology (Clinical Unit) under full medical and nursing supervision.

A schedule of all study assessments is provided in Table 10.9.1, Table 10.9.2 and Table 10.9.3.

Part A (SAD)

Up to 5 dose levels of AX-158 are planned to be investigated in Part A of the study (with an option to include additional dose levels to a maximum of 2 cohorts). Each cohort will follow a dose-leader schedule; two participants (one randomised to receive placebo and one randomised to receive AX-158) will be dosed in a blinded manner at least 24 hours prior to the remainder of the cohort. In the absence of any safety concerns in these first 2 participants, dosing of the remainder of the cohort will proceed on a parallel study schedule.

The lowest dose of AX-158 will be evaluated first; refer to [Section 10.8.7](#) for further details; dose administration in the subsequent cohort will only proceed after blinded review of available safety and PK data from a minimum of six (6) evaluable participants in the preceding cohort by the DERC; see [Section 10.3](#) for full details. The maximum dose investigated will not exceed a level anticipated to result in a C_{\max} or AUC_{0-24} exceeding those observed at NOAEL levels in the most relevant non-clinical species without prior approval by the REC and MHRA (via substantial amendment). The study may be discontinued at any time if any unacceptable safety findings are identified (as determined by PI and Sponsor).

Screening (Days -28 to Day -2)

Screening assessments will be performed from Day -28 to Day -2 to ensure the eligibility of participants. Assessments will be performed as per Table 10.9.1

Treatment Period (Day -1 to Post-Treatment 3 (i.e., Day 4))

Participants will be admitted to the Clinical Unit on the morning of Day -1 with confirmation of eligibility and baseline assessments performed as per Table 10.9.1. Randomisation will occur prior to dose on Day 1.

After an overnight fast of at least 10 h, dose administration will occur on the morning of Day 1. Fasting will continue until 4 h post-dose; a standardised meal will then be provided. Clinical and laboratory assessments of safety, tolerability and PK variables will be conducted throughout the in-house period as per Table 10.9.1. Participants will be discharged from the clinical unit following completion of 72 h post-dose assessments providing there are no ongoing safety concerns; participants may be monitored as an outpatient where the PI (or delegate) deems this to be appropriate.

A follow-up visit will be conducted 5-7 days following the first dose of AX-158 or placebo (i.e., Day 8) as per Table 10.9.1.

Post-Study Follow Up Visit (5-7 days after last dose of IMP (i.e., Day 8)).

For participants in all SAD cohorts, a follow-up visit will be conducted 5-7 days following last IMP or placebo administration (i.e., Day 8). If all follow-up assessments (Table 10.9.1) are satisfactory the PI (or delegate), will discharge the participant from the study. If any AEs are ongoing, or any assessments are not satisfactory, participants may be recalled to the unit for follow-up assessments until the PI (or delegate) is satisfied the participant is medically stable and may be discharged from the study. Participants will be advised to return or contact the unit at any time if they may be experiencing any adverse effects.

Following DERC review of data from Part A, the dose for participants in Part B will be determined.

Part B (Food Effect)

The dose to be evaluated in the food-effect cohort will be determined based on review of all available safety, tolerability, and PK data from Part A. Participants in the food-effect cohort will receive AX-158 administered under both fasted and fed conditions.

Where receiving a dose in the fed state, participants will be provided the standard FDA high fat breakfast^[5] which should be consumed within 30 minutes (mins) or less, with study drug administration occurring approximately 30 mins after the start of the meal. Fasting will recommence until 4 h post-dose; a standardised meal will then be provided.

Participants will be discharged from the clinical unit following completion of 72 h post-dose assessments providing there are no ongoing safety concerns; participants will be monitored as an outpatient.

Treatment Periods (Day -1 to Day 4): Participants will receive a single dose of AX-158 over 2 treatments periods in fed/faasted conditions (1 condition per period). Each treatment period will be approximately 4 days duration, from the morning before dosing (Day -1) until 72 h post-dose (Day 4). During each treatment period, participants will receive a single dose of AX-158 following an overnight fast of at least 10 h OR following consumption of a high-fat breakfast over 2 treatment periods (1 per period). When receiving AX-158 in the fed state, following an overnight fast of at least 10 h, participants will be provided the standard FDA high fat breakfast which will be served and consumed within 30 mins. AX-158 should be administered 30 mins after the start of the meal. At both treatment periods, fasting will continue/recommence until 4 h post-dose; a standardised meal will then be provided. Participants will be discharged 72 h post-dose. PK samples will be collected pre-dose and up to 72 h post-dose for the measurement of AX-158. Safety will also be evaluated at time points specified in Table 10.9.2. There will be at least 7 days between dose administrations.

Following DERC review of data from Part B, the dose for participants in Part C will be determined, and cohorts in Part C may be administered AX-158 under fasted or fed conditions as deemed appropriate, pending DERC determination of any appreciable impact of food on the absorption, distribution, metabolism, and excretion (ADME) of AX-158.

A follow-up visit will be conducted 5-7 days following last IMP administration. If all follow-up assessments (Table 10.9.2) are satisfactory the PI (or delegate), will discharge the participant from the study. If any AEs are ongoing, or any assessments are not satisfactory, participants may be recalled to the unit for follow-up assessments until the PI (or delegate) is

satisfied the participant is medically stable and may be discharged from the study. Participants will be advised to return or contact the unit at any time if they may be experiencing any adverse effects.

Part C (MAD)

Part C will be initiated following review of all available safety, tolerability, and PK data from Part A (SAD) and Part B (Food Effect) to determine the appropriate AX-158 dose and dosage regimen to be evaluated in the initial MAD cohort; the starting dose in Part C will not exceed the highest dose level examined in the preceding completed Part A cohorts or a dose level expected to exceed the highest AX-158 exposure (C_{max} and AUC_{0-24}) observed from preceding Part A cohorts. It is planned to dose AX-158 or placebo once daily for at least 10 consecutive days; doses, dosing duration and dose regimen (i.e., q.i.d., b.i.d., t.i.d.) of AX-158 and matching placebo for Part C may be modified based on all available safety, tolerability, and PK data and applied to additional MAD cohorts. The maximum dose will not exceed a level anticipated to result in a C_{max} or AUC_{0-24} exceeding those observed at NOAEL levels in the most relevant non-clinical species without prior approval by the REC and MHRA (via substantial amendment).

Up to 3 dose levels of AX-158 are planned to be investigated in Part C of the study (with an option to include additional dose levels to a maximum of 2 cohorts). Each cohort will follow a dose-leader schedule in which two participants (one randomised to receive placebo and one randomised to receive AX-158) will be dosed at least 24 h prior to the remainder of the cohort allowing for review of emerging safety and tolerability data from this dose-leader group on an ongoing basis and to avoid dosing all participants in a cohort simultaneously.

The lowest dose level of AX-158 will be evaluated first; dose administration in the subsequent cohorts will only proceed after blinded safety, tolerability, and PK data from a minimum of 6 evaluable participants in the preceding cohort have been reviewed by the DERC; see [Section 10.3](#) for full details). The study part may be discontinued at any time if any unacceptable safety findings are identified (as determined by PI and Sponsor).

Screening (Days -28 to Day -2)

Screening assessments will be performed from Day -28 to Day -2 to ensure the eligibility of participants. Assessments will be performed as per Table 10.9.3.

In-patient Period (Day -1 to Post-Treatment 3 (i.e., Day 13))

Participants will be admitted to the Clinical Unit on the morning of Day-1 with confirmation of eligibility and baseline assessments performed as per Table 10.9.3. Randomisation will occur prior to dose on Day 1. An evening snack will be consumed at least 10 h before each dose administration. After an overnight fast of at least 10 h, dose administration will occur each day, on the morning of Day 1 to Final Dosing Day (planned as Day 10). It is planned to administer doses in Part C in a fasted state, however following review of Part B food-effect data, the dose *may* be administered in a fed state with a standardised meal. Fasting will continue until 4 h post-dose; a standardised meal will then be provided. Clinical and laboratory assessments of safety, tolerability and PK variables will be conducted throughout the in-house period as per Table 10.9.3.

Participants will be discharged from the Clinical Unit on Post-Treatment (i.e., Day 13) following the completion of the 72 h post-last dose assessments providing there are no ongoing safety concerns.

Post-Study Follow Up Visit (5-7 days after final dose of IMP i.e., Day 17).

For participants in all MAD cohorts, a follow-up visit will be conducted 5-7 days following last IMP or placebo administration. If all follow-up assessments (Table 10.9.3.) are satisfactory the PI (or delegate), will discharge the participant from the study. If any AEs are ongoing, or any assessments are not satisfactory, participants may be recalled to the unit for follow-up assessments until the PI (or delegate) is satisfied the participant is medically stable and may be discharged from the study. Participants will be advised to return or contact the unit at any time if they may be experiencing any adverse effects.

10.2 Adaptive Elements

This study is designed to be adaptive, and the following elements may be revised based on emerging clinical safety and PK data throughout the course of the trial without a substantial amendment:

- Following review of the Part B Food effect cohort PK data, participants in Part C cohorts may be administered AX-158 under fasted or fed conditions, as deemed appropriate, pending DERC determination of any appreciable impact of food effect of AX-158. If food effect is seen, cohorts in Part C could be dosed with a standardised meal (as opposed to the high-fat breakfast). This decision will be documented in the Food Effect Cohort Dose Escalation Review meeting minutes.
- The timing, type, and number of safety, PK assessments may be modified (without extending the duration of the study).
- A minimum washout of 7 days is expected within Part B but *may* be extended based on emerging safety and PK data to 14 days.
- The number and/or volume of blood samples per assessment may be increased as long as the total volume of blood drawn for a participant does not exceed 10% of the pre-specified total blood volume or surpass 500 mL (except when extra blood samples need to be taken for safety reasons).
- In Part C (MAD), it is planned to dose AX-158 or placebo once daily for at least 10 consecutive days; doses, dosing duration and dose regimen (i.e., q.i.d., b.i.d, t.i.d) of AX-158 and matching placebo for Part C *may* be modified based on all available safety, tolerability, and PK data and applied to additional MAD cohorts up to a maximum of 14 days.
- Dose levels/dosing regimen *may* be adjusted lower based on emerging safety and PK data.
- Additional dose level(s) *may* be examined if deemed safe and appropriate. These cohorts will enrol 8 participants (for SAD cohorts) and up to 8 participants (for MAD cohorts).
- Currently it is planned that in order to dose escalate between cohorts and between study parts, PK data from up to the 24 hr post-last time point in all parts and 72 hr post-last dose safety data is required. However, if during the course of dose escalation, it is

determined necessary to do so, then dose escalation procedures may be extended in order to include additional PK data up to the 72 hr post-last dose time point in all study parts.

- Exploratory PD samples will be taken pre-dose in Part A (SAD) and Part C (MAD) additional sample(s) will be taken based on emerging data. The total blood volume will not exceed 500mL.

10.3 Dose Escalation Procedures and Stopping Criteria

10.3.1 Dose Escalation Procedures

Following completion of each cohort, a summary of all relevant safety AEs, ECG, vital signs, laboratory assessments up to 72 h post dose) and PK data (up to 24 h post-dose for Part A & Part B and 10 days for Part C) will be produced on behalf of the Principal Investigator. Planned doses may be modified following a review of emerging data. Progression to the next SAD dose level and dose selection will be based on the available safety and PK data from at least 6 evaluable participants from the preceding dose level. Progression to the next MAD dose level and dose selection will be based on the available safety and PK data from at least 6 evaluable participants from the preceding dose level. An evaluable participant is defined as a participant who has received the planned dose (active or placebo) and has sufficient PK samples to estimate C_{max} and AUC_{0-24} . Dose escalation will be dependent upon generation of acceptable safety (and PK) data. If it is not appropriate to escalate the dose according to the proposed dose escalation schedule, then the same dose, an intermediate dose or a lower dose may be given following discussion between the Sponsor and the Principal Investigator (or deputy) if no stopping criteria are met.

There will be a Telephone Conference at a pre-appointed time to involve the Simbec-Orion Project Manager and Principal Investigator (or deputy) and the Sponsor's representative(s), including the Sponsor's Responsible Physician. After discussion of all the data, the decision will be made whether to dose escalate and a written document (dose escalation approval form) signed by the Principal Investigator (or deputy) and Sponsor will be produced ratifying that decision. Full minutes, to be agreed by all parties, will be produced for each discussion regarding dose escalation and filed in the Investigator Site File. A copy of the signed dose escalation approval form will be provided to the Simbec-Orion IMP Management team to allow the release of the next dose level of IMP to the clinic.

Dose escalation stopping criteria are detailed in [Section 10.3.4](#)

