8.7 Risk Assessment

The risk of this proposed Phase I study is considered acceptable given that:

- There were no adverse events seen in non-clinical species above the NOAEL which warrant specific monitoring of participants.
- The proposed starting dose of AX-158 in humans (5 mg/day) is 29 times lower than the HED of NOAEL from the most sensitive species (the rat) and the starting dose is predicted to achieve total exposures 3x-fold lower than the lowest efficacious exposure achieved in the mouse at 1 mg/kg, an approximately 121-fold lower total C_{max} , and 69-fold lower total AUC than exposure achieved at the NOAEL in rats and 78-fold lower total male C_{max} , and 41-fold lower total AUC than exposure achieved at the NOAEL in minipigs.
- The starting dose in Part C (multiple ascending dose [MAD]) will not exceed the highest dose examined in the preceding completed Part A (single ascending dose [SAD]) cohorts or a level expected to exceed the highest AX-158 exposure (C_{max} and AUC_{0-24}) observed from preceding Part A (SAD) cohorts.
- For each SAD and MAD cohort, 2 sentinel participants (1 active, 1 placebo) will be dosed and monitored for 24 h prior to dosing the rest of the cohort.
- In Part A (SAD), dose escalation will be done in a stepwise, controlled manner, with dose escalation only being permitted after full evaluation of up to 24 h PK and 72 h safety data from the previous cohort by the Dose Escalation Review Committee (DERC).
- In Part C (MAD) dose escalation will be done in a stepwise, controlled manner, with dose escalation only being permitted after full evaluation of up to 10 days PK and safety data from the previous cohort by the DERC.
- The study is being conducted in a Medicines and Healthcare products Regulatory Agency (MHRA) accredited Phase I unit.

Further details of the non-clinical studies and a summary of the known and potential risks and benefits to human participants of AX-158 can be found in the Investigator's Brochure (IB)^[2].

The study will be conducted in compliance with the protocol, GCP and the applicable regulatory requirement(s), as indicated within Section 6.2.5 of the ICH GCP E6 (R2) guidelines^[2].

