7 SAFETY MONITORING

Following completion of each cohort, a summary of all relevant safety AEs, ECG, vital signs, laboratory assessments up to 72 h post dose) and PK data (up to 24 h post-dose for Part A & Part B and 10 days for Part C) will be produced on behalf of the Principal Investigator. Planned doses may be modified following a review of emerging data. Progression to the next SAD dose level and dose selection will be based on the available safety and PK data from at least 6 evaluable participants from the preceding dose level. Progression to the next MAD dose level and dose selection will be based on the available safety and PK data from at least 6 evaluable participants from the preceding dose level. An evaluable participant is defined as a participant who has received the planned dose (active or placebo) and has sufficient PK samples to estimate C_{max} and AUC_{0-24} . Dose escalation will be dependent upon generation of acceptable safety (and PK) data. If it is not appropriate to escalate the dose according to the proposed dose escalation schedule, then the same dose, an intermediate dose or a lower dose may be given following discussion between the Sponsor and the Principal Investigator (or deputy) if no stopping criteria are met.

Outputs for the safety review will be presented as Excel listings of the clinical database.

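### Part C escalation: the safety cut-off is stated in three ways, and the definition of an evaluable participant names no dosing day

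*Protocol*

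**What the plan says.** **Data needed before Part C escalates.**

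- Protocol 10.2, repeated in the synopsis, covers every part: "PK data from up to the 24 hr post-last time point in all parts and 72 hr post-last dose safety data is required". For a 10-day cohort, 10.1 puts the final in-house assessments on Day 13, with discharge "following the completion of the 72 h post-last dose assessments".
- Protocol 8.7 allows Part C escalation only after "full evaluation of up to 10 days PK and safety data from the previous cohort by the DERC". The Part A bullet in the same list asks for "full evaluation of up to 24 h PK and 72 h safety data from the previous cohort", which agrees with 10.2.
- Protocol 10.3.1 describes a summary drawn up once each cohort is complete. It takes safety data to 72 h after dosing, without saying which dose. For exposure it says "PK data (up to 24 h post-dose for Part A & Part B and 10 days for Part C) will be produced". SAP Section 7 has the same safety window and the same exposure wording: "PK data (up to 24 h post-dose for Part A & Part B and 10 days for Part C".

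**Who counts.** Under 10.3.1, progression in Part A and in Part C is "based on the available safety and PK data from at least 6 evaluable participants from the preceding dose level". An evaluable participant is one "who has received the planned dose (active or placebo) and has sufficient PK samples to estimate" Cmax and AUC0-24. SAP Section 7 repeats the definition. Protocol 10.11.2 derives both parameters in Part C on Day 1 and again on the final dosing day. SAP 6.3 lets a valid Day 1 profile admit a Part C participant to the PK Set, but requires all doses for the Day 10 analysis. The escalation count draws no such line.

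**The concern.** Part C is the first repeat dosing of AX-158 in humans, so its escalation decisions should rest on repeat-dose data with one clear cut-off. Two things blur this.

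First, the Part C bullet in 8.7 departs from the rule in 10.2, while the Part A bullet beside it does not. The 10.3.1 wording does not settle the matter, because 72 h after dosing is ambiguous when there are ten doses. The one explicit post-last-dose rule sits in 10.2 as the current plan, within a list of elements that may change without a substantial amendment. The only change named there is an extension of the PK data. The hours at issue hold ECGs and a laboratory panel that feed the QTcF and liver criteria in 10.3.4.

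Second, the evaluable definition fits a single-dose cohort and is carried unchanged into a multiple-dose one. Participants with only a Day 1 profile will mostly be those who stopped early. 10.8.9 bars escalation if any individual exceeds the exposure limits, but it can test observed exposure only in profiles that exist.

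**Working it through.** **Inputs.** Once-daily dosing on Days 1 to 10 and discharge on Day 13 (10.1); 14-day maximum (10.2); eight per cohort, six active and two placebo (10.1); six evaluable needed (10.3.1). Part C assessment times are in SAP 11.6.2 to 11.6.4. Predicted AUC is 3.04 µg·h/mL at 40 mg and the AUC limit is 14.859 µg·h/mL (10.8.7). Half-life is not given.

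**1. The plan's own day.** Dose n falls at (n − 1) × 24 h, so dose 10 is at 216 h. Adding 72 h gives 288 h; 288/24 + 1 = Day 13, as 10.1 states.

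**2. Safety gap in 8.7 read alone.** The longest reading of ten days is 10 × 24 = 240 h from first dose. The gap to the 10.2 rule is 288 − 240 = 48 h. If the ten days end at the Day 10 pre-dose point (216 h), the gap is 72 h. So 48 h is the minimum.

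**3. PK gap.** 10.2 needs PK to 216 + 24 = 240 h. On the 240 h reading the gap is 0 h, so the ten-day PK wording agrees with 10.2 for a 10-day cohort.

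**4. Optional 14-day regimen.** Dose 14 is at 13 × 24 = 312 h. Ten days then end 312 − 240 = 72 h before the last dose and 312 + 72 − 240 = 144 h before the 10.2 safety cut-off.

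**5. What lies between 240 h and 288 h.** Vital signs at 36, 48 and 72 h after the last dose (3), ECG at 48 and 72 h (2), laboratory panel at 72 h (1): six scheduled assessments. As a check that the 72 h panel follows both profile days: Day −1 (1) + 24 h and 72 h after Day 1 and after Day 10 (4) + mid-dosing (1) + follow-up (1) = 7, the number in protocol Table 10.9.6.

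**6. When the evaluable wording changes a decision.** If k of n participants lack a final-day profile, Day 1 profiles are needed to reach six only when n − k < 6. For n = 8 this needs k ≥ 3; for n = 6, k ≥ 1. Six evaluable from a full cohort include at least 6 − 2 = 4 on active drug.

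**7. What a Day 1 profile can miss.** With mono-exponential decline, the Day 10/Day 1 AUC0-24 ratio is (1 − r^10)/(1 − r), where r = 2^(−24/t½). At assumed half-lives of 4, 8, 12, 24 and 48 h it is 1.02, 1.14, 1.33, 2.00 and 3.31. With first-order absorption (assumed ka 1/h), the 48 h value is 3.43.

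**8. Against the limit.** 14.859/3.04 = 4.9. Taking the predicted AUC as a single-dose value, 3.04 × 3.43 = 10.4. The SAP shells show Part A Cohort 5 at 50 mg; linear scaling gives 3.04 × 50/40 = 3.8, and 3.8 × 3.43 = 13.0. Both are below 14.859.

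**The case against.** The strongest reply on the cut-off is that 8.7 is a risk summary stating a necessary condition. Meeting the stricter rule in 10.2 meets 8.7 as well. The ten days there may also qualify only the PK data, leaving safety without a cut-off in that bullet. The operative section, 10.3.1, already asks for 72 h of safety data after cohort completion, and SAP Section 7 repeats it. A reader might infer that 8.7 authorises escalation 48 h early. The documents do not support that, because 10.2 states its own data as required. This objection stands, and it reduces the point to an inconsistency.

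On the count, the planned dose in Part C can naturally mean the full regimen, and 10.2 expects PK to 24 h after the last dose in all parts. A reader might infer that the plan requires no final-day profiles. That is true of the definition taken by itself, but not of the escalation rules as a whole. What remains is that no section sets a minimum number of final-day profiles, and the wording admits the weaker reading.

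The scenario is also narrow. Dosing is in-house and supervised, 10.7.4 leaves replacement open for withdrawals other than those due to significant drug-related adverse events, and 10.3.4 and 10.8.9 apply throughout. The accumulation figures rest on assumed half-lives and show no breach at the doses considered, so they illustrate what a Day 1 profile leaves out and are not evidence of a hazard.

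**Conclusion.** The point holds as a minor one. Three differently worded safety cut-offs govern the same Part C decision, and the evaluable definition does not fit a multiple-dose cohort. Read alone, 8.7 ends at least 48 h before the data that 10.2 requires; the PK wording is out of step only for a 14-day regimen. The evaluable wording could affect a decision only if three of eight participants lack a final-day profile, or one in a cohort of six, which the SAP's allowance of up to eight permits.

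This assumes once-daily dosing and time counted from each participant's own first dose. It also depends on version. The protocol reviewed is V4.0, while SAP 1.1 says the SAP was written to V5.0, which is not available. SAP Section 7 carries the evaluable definition, the 72 h safety window and the ten-day PK wording. The 8.7 and 10.2 texts still need checking against V5.0.

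**What to change.** In protocol 8.7 and 10.3.1 and in SAP Section 7, state for Part C: *PK to 24 h and safety to 72 h after the final dose*. This agrees with 10.2 and also covers a 14-day regimen.

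Add to the evaluable definition in 10.3.1 and SAP Section 7: *In Part C, a participant counts only after taking every planned dose and providing enough final-dosing-day samples to derive Cmax and AUC0-24. Safety data from those who stop early are still reviewed.*

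State what follows if fewer than six qualify: either escalation is held until the Dose Escalation Review Committee documents a decision, or replacement is allowed for this purpose. Without this the tighter definition could deadlock. In a cohort of six, one withdrawal for a significant drug-related adverse event leaves five, and 10.7.4 bars replacement.

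The cost is wording in two protocol sections and one SAP section, with no new samples for 10-day dosing. A review may move by one to three days if Day 10 was the working cut-off, and early withdrawals may cause a hold.
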